15.3.1 Study Design

Figure 2 gives study design flow charts for ORR, OS, and Figure 1 shows the overall testing procedure for ORR, OS and PFS where PFS will be tested in IMDC I/P-risk and all-risk populations sequentially after statistical significance of OS in both populations. All p-values and testing levels are two-sided in this section and one-sided in Section 15.3.3. At interim analysis, if OS in IMDC I/P-risk population is not statistically significant at 0.01 level, then number of events in this population for the final analysis will be re-estimated based on the pre-specified adaptation rule. The final analysis will be triggered by the required number of events in the IMDC I/P risk population. At final analysis, if OS in IMDC I/P risk population is statistically significant (at 0.0462 level if ORR is not significant at IA and at 0.0472 level if ORR is significant at IA), then OS in IMDC all-risk population will also be tested at the same level as the IMDC I/P risk population. Given the statistical significance of OS in the IMDC all-risk population at FA, the key secondary endpoint of PFS by BICR in the IMDC I/P-risk population and the IMDC all-risk population will be test sequentially at level 0.0323 if ORR is not significant at IA and at level 0.0335 if ORR is significant at IA.

On the other hand, if OS in IMDC I/P risk population is statistically significant at 0.01 level at interim, then formal efficacy claim can be obtained, and no further testing will be performed for this population. At the same time, OS in the IMDC all-risk population can also tested at 0.01 level. If statistically significant, the key secondary endpoint of PFS by BICR in both populations will be tested sequentially at 0.03 level. Otherwise, if OS in all-risk population is not significant, number of events in this population for the final analysis will be re-estimated based on the pre-specified adaptation rule. The final analysis occurs when the adapted number of events in the IMDC all-risk population is achieved. The OS in IMDC all-risk population will be tested at 0.0462 level if ORR is not significant at IA and at 0.0472 level if ORR is significant at IA. And the key secondary endpoint of PFS by BICR in the two populations will be tested sequentially at level 0.0323 if ORR is not significant at IA and at level 0.0335 if ORR is significant at IA, given the statistical significance of OS in all-risk population at final analysis.

15.3.2 Notation and Test Statistics

For OS in the IMDC I/P-risk populatio, let T_1 denote the interim logrank test statistic with d_1 number of events and T_2 denote the regular logrank test statistic based on the cumulative data at final analysis with adapted d_2^* number of events. Then we calculate the incremental test statistic following Wassmer (2006):

$$\tilde{T}_2^* = \frac{\sqrt{d_2^*}T_2 - \sqrt{d_1}T_1}{\sqrt{d_2^* - d_1}}.$$

The final weighted test statistic with weight $\sqrt{2/3}$ and $\sqrt{1/3}$ can be written as

$$T_2^* = \sqrt{2/3}T_1 + \sqrt{1/3}\tilde{T}_2^*.$$

Similarly for OS in the IMDC all-risk population, let T_1^a denote the interim logrank test statistic with d_1^a number of events, let T_2^{a*} denote the logrank test statistic based on the cumulative data at final analysis with d_2^{a*} number of events resulting from adaption in the IMDC I/P population and T_2^{a**} denote the logrank test statistic based on the cumulative data at final analysis with d_2^{a**} number of events resulting from adaption in the IMDC all-risk population. Then the corresponding incremental test statistics could be calculated as follows:

$$\tilde{T}_2^{a*} = \frac{\sqrt{d_2^{a*}T_2^{a*}} - \sqrt{d_1^aT_1^a}}{\sqrt{d_2^{a*} - d_1^a}} \quad \text{or} \quad \tilde{T}_2^{a**} = \frac{\sqrt{d_2^{a**}T_2^{a**}} - \sqrt{d_1^aT_1^a}}{\sqrt{d_2^{a**} - d_1^a}}.$$

The final test statistics can be written as

$$T_2^{a*} = \sqrt{2/3}T_1^a + \sqrt{1/3}\tilde{T}_2^{a*} \quad \text{or} \quad T_2^{a**} = \sqrt{2/3}T_1^a + \sqrt{1/3}\tilde{T}_2^{a**}.$$

Following a similar logic, we denote the interim test statistics for PFS in I/P and all-risk populations as Z_1 and Z_1^a , denote the final test statistics for PFS in both populations as Z_2^* , Z_2^{a*} based on adaption in the IMDC I/P population with event size d_2^{a*} , and Z_2^{**} and Z_2^{a**} based on adaption in the IMDC all-risk population with event size d_2^{a**} .

Further, let H_{01}^{OS} and H_{02}^{OS} denote the null hypotheses regarding the OS in IMDC I/P-risk and IMDC all-risk population, H_{01}^{ORR} and H_{02}^{ORR} denote the null hypotheses regarding the ORR in IMDC I/P-risk and IMDC all-risk population, and H_{01}^{PFS} and H_{02}^{PFS} denote the null hypotheses regarding the PFS in IMDC I/P-risk and IMDC all-risk population.

15.3.3 Strong Control of Family-wise Error Rate

By the partition principle, the family-wise error rate is strongly controlled at one-sided level 0.025 if the probability of false rejection in each of the following partitioned parameter space could be controlled at the same one-sided 0.025 level. Although there are six individual hypotheses: H_{01}^{OS} , H_{02}^{OS} , H_{01}^{ORR} , H_{02}^{ORR} , H_{01}^{PFS} , and H_{02}^{PFS} , due to the decision path between H_{01}^{OS} , H_{02}^{OS} , H_{01}^{PFS} , H_{02}^{PFS} and the decision path between H_{01}^{ORR} and H_{02}^{ORR} , there are only a total of $3*5-1=14$ partitioned parameter spaces (Liu and Hsu 2009).

Partitioned parameter space (where \cdot^C denotes the complement of the null space)	False rejection
1. $H_{01}^{ORR} \cap H_{01}^{OS}$	Reject H_{01}^{ORR} or H_{01}^{OS}
2. $(H_{01}^{ORR})^C \cap H_{02}^{ORR} \cap H_{01}^{OS}$	Reject H_{02}^{ORR} or H_{01}^{OS}
3. $H_{01}^{ORR} \cap (H_{01}^{OS})^C \cap H_{02}^{OS}$	Reject H_{01}^{ORR} or H_{02}^{OS}
4. $(H_{01}^{ORR})^C \cap H_{02}^{ORR} \cap (H_{01}^{OS})^C \cap H_{02}^{OS}$	Reject H_{02}^{ORR} or H_{02}^{OS}
5. $(H_{01}^{ORR})^C \cap (H_{02}^{ORR})^C \cap H_{01}^{OS}$	Reject H_{01}^{OS}
6. $(H_{01}^{ORR})^C \cap (H_{02}^{ORR})^C \cap (H_{01}^{OS})^C \cap H_{02}^{OS}$	Reject H_{02}^{OS}
7. $H_{01}^{ORR} \cap (H_{01}^{OS})^C \cap (H_{02}^{OS})^C \cap H_{01}^{PFS}$	Reject H_{01}^{ORR} or H_{01}^{PFS}
8. $(H_{01}^{ORR})^C \cap H_{02}^{ORR} \cap (H_{01}^{OS})^C \cap (H_{02}^{OS})^C \cap H_{01}^{PFS}$	Reject H_{02}^{ORR} or H_{01}^{PFS}
9. $(H_{01}^{ORR})^C \cap (H_{02}^{ORR})^C \cap (H_{01}^{OS})^C \cap (H_{02}^{OS})^C \cap H_{01}^{PFS}$	Reject H_{01}^{PFS}
10. $H_{01}^{ORR} \cap (H_{01}^{OS})^C \cap (H_{02}^{OS})^C \cap (H_{01}^{PFS})^C \cap H_{02}^{PFS}$	Reject H_{01}^{ORR} or H_{02}^{PFS}
11. $(H_{01}^{ORR})^C \cap H_{02}^{ORR} \cap (H_{01}^{OS})^C \cap (H_{02}^{OS})^C \cap (H_{01}^{PFS})^C \cap H_{02}^{PFS}$	Reject H_{02}^{ORR} or H_{02}^{PFS}
12. $(H_{01}^{ORR})^C \cap (H_{02}^{ORR})^C \cap (H_{01}^{OS})^C \cap (H_{02}^{OS})^C \cap (H_{01}^{PFS})^C \cap H_{02}^{PFS}$	Reject H_{02}^{PFS}
13. $H_{01}^{ORR} \cap (H_{01}^{OS})^C \cap (H_{02}^{OS})^C \cap (H_{01}^{PFS})^C \cap (H_{02}^{PFS})^C$	Reject H_{01}^{ORR}
14. $(H_{01}^{ORR})^C \cap H_{02}^{ORR} \cap (H_{01}^{OS})^C \cap (H_{02}^{OS})^C \cap (H_{01}^{PFS})^C \cap (H_{02}^{PFS})^C$	Reject H_{02}^{ORR}

- Under partitioned parameter spaces 1 or 2 (with j=1 or 2),

$$\begin{aligned}
 P(\text{false rejection}) &= P(\text{Reject } H_{0j}^{ORR} \text{ or } H_{0j}^{OS}) \\
 &= P(\text{Reject } H_{0j}^{ORR}) + P(\text{Reject } H_{0j}^{OS} \text{ but do not reject } H_{0j}^{ORR}) \\
 &\leq 0.0005 + P(T_1 > z_{0.005} \text{ or } T_2^* > z_{0.0462/2}) \\
 &= 0.0005 + P(T_1 > z_{0.005}) + P(T_1 \leq z_{0.005} \text{ and } T_2^* > z_{0.0462/2}) \\
 &= 0.0005 + 0.005 + 0.0195 = 0.025
 \end{aligned}$$

since T_1 and T_2^* asymptotically follows standard bivariate normal distribution with correlation $\sqrt{2/3}$. (Wassmer, 2006)

- Under partitioned parameter space 3 or 4 (with j=1 or 2),

$$\begin{aligned}
 P(\text{false rejection}) &= P(\text{Reject } H_{0j}^{ORR} \text{ or } H_{0j}^{OS}) \\
 &= P(\text{Reject } H_{0j}^{ORR}) + P(\text{Reject } H_{0j}^{OS} \text{ but do not reject } H_{0j}^{ORR}) \\
 &\leq 0.0005 + P(T_1 > z_{0.005}, T_1^a > z_{0.005}) \\
 &\quad + P(T_1 > z_{0.005}, T_1^a \leq z_{0.005}, T_2^{a**} > z_{0.0462/2}) \\
 &\quad + P(T_1 \leq z_{0.005}, T_2^* > z_{0.0462/2}, T_2^{a*} > z_{0.0462/2}) \\
 &\leq 0.0005 + P(T_1 > z_{0.005}, T_1^a > z_{0.005}) \\
 &\quad + P(T_1 > z_{0.005}, T_1^a \leq z_{0.005}, T_2^{a**} > z_{0.0462/2}) \\
 &\quad + P(T_1 \leq z_{0.005}, T_2^{a*} > z_{0.0462/2})
 \end{aligned}$$

$$\begin{aligned}
&\leq 0.0005 + P(T_1 > z_{0.005}, T_1^a > z_{0.005}) \\
&+ P(T_1 > z_{0.005}, T_1^a \leq z_{0.005}, T_2^{a**} > z_{0.0462/2}) \\
&+ P(T_1 \leq z_{0.005}, T_1^a > z_{0.005}) + P(T_1 \leq z_{0.005}, T_1^a \leq z_{0.005}, T_2^{a*} > z_{0.0462/2}) \\
&= 0.0005 + P(T_1^a > z_{0.005}) + P(T_1 > z_{0.005}, T_1^a \leq z_{0.005}, T_2^{a**} > z_{0.0462/2}) \\
&+ P(T_1 \leq z_{0.005}, T_1^a \leq z_{0.005}, T_2^{a*} > z_{0.0462/2}) \\
&= 0.0005 + 0.005 + P(T_1 > z_{0.005}, T_1^a \leq z_{0.005}, \sqrt{2/3}T_1^a + \sqrt{1/3}\tilde{T}_2^{a**} > z_{0.0462/2}) \\
&+ P(T_1 \leq z_{0.005}, T_1^a \leq z_{0.005}, \sqrt{2/3}T_1^a + \sqrt{1/3}\tilde{T}_2^{a*} > z_{0.0462/2})
\end{aligned}$$

By Wassmer (2006), the conditional null distribution of \tilde{T}_2^{a*} and \tilde{T}_2^{a**} given the interim data $(T_1$ and $T_1^a)$ approximately equals standard normal distribution, denoted as $\tilde{T}_2^{a*}|(T_1, T_1^a)$

$\stackrel{d}{\Leftrightarrow} \tilde{T}_2^{a**}|(T_1, T_1^a) \stackrel{d}{\Leftrightarrow} T \sim N(0, 1)$. Therefore, the following joint distributions are the same: $(T_1, T_1^a, \tilde{T}_2^{a*}) \stackrel{d}{\Leftrightarrow} (T_1, T_1^a, \tilde{T}_2^{a**}) \stackrel{d}{\Leftrightarrow} (T_1, T_1^a, T)$. Subsequently, the following joint distributions are also the same:

$$(T_1, T_1^a, \sqrt{2/3}T_1^a + \sqrt{1/3}\tilde{T}_2^{a*}) \stackrel{d}{\Leftrightarrow} (T_1, T_1^a, \sqrt{2/3}T_1^a + \sqrt{1/3}\tilde{T}_2^{a**}) \stackrel{d}{\Leftrightarrow} (T_1, T_1^a, \sqrt{2/3}T_1^a + \sqrt{1/3}T) \quad (1)$$

Hence, above = $0.0055 + P(T_1 > z_{0.005}, T_1^a \leq z_{0.005}, \sqrt{2/3}T_1^a + \sqrt{1/3}T > z_{0.0462/2})$

$$+ P(T_1 \leq z_{0.005}, T_1^a \leq z_{0.005}, \sqrt{2/3}T_1^a + \sqrt{1/3}T > z_{0.0462/2}).$$

$$= 0.0055 + P(T_1^a \leq z_{0.005}, \sqrt{2/3}T_1^a + \sqrt{1/3}T > z_{0.0462/2})$$

$$= 0.025.$$

- Under partitioned parameter space 5,

$$P(\text{false rejection}) = P(\text{Reject } H_{01}^{OS}) \leq P(T_1 > z_{0.005} \text{ or } T_2^* > z_{0.0472/2}) = 0.025$$

- Under partitioned parameter space 6,

$$P(\text{false rejection}) = P(\text{Reject } H_{02}^{OS}) \leq P(T_1 > z_{0.005}, T_1^a > z_{0.005})$$

$$+ P(T_1 > z_{0.005}, T_1^a \leq z_{0.005}, T_2^{a**} > z_{0.0472/2})$$

$$+ P(T_1 \leq z_{0.005}, T_2^* > z_{0.0472/2}, T_2^{a*} > z_{0.0472/2})$$

$$\leq P(T_1 > z_{0.005}, T_1^a > z_{0.005}) + P(T_1 > z_{0.005}, T_1^a \leq z_{0.005}, T_2^{a**} > z_{0.0472/2})$$

$$+ P(T_1 \leq z_{0.005}, T_2^{a*} > z_{0.0472/2})$$

$$= P(T_1 > z_{0.005}, T_1^a > z_{0.005}) + P(T_1 > z_{0.005}, T_1^a \leq z_{0.005}, T_2^{a**} > z_{0.0472/2})$$

$$+ P(T_1 \leq z_{0.005}, T_1^a > z_{0.005}, T_2^{a*} > z_{0.0472/2}) + P(T_1 \leq z_{0.005}, T_1^a \leq z_{0.005}, T_2^{a**} > z_{0.0472/2})$$

$$\leq P(T_1 > z_{0.005}, T_1^a > z_{0.005}) + P(T_1 > z_{0.005}, T_1^a \leq z_{0.005}, T_2^{a**} > z_{0.0472/2})$$

$$\begin{aligned}
 &+ P(T_1 \leq z_{0.005}, T_1^a > z_{0.005}) + P(T_1 \leq z_{0.005}, T_1^a \leq z_{0.005}, T_2^{a*} > z_{0.0472/2}) \\
 &= P(T_1^a > z_{0.005}) + P(T_1 > z_{0.005}, T_1^a \leq z_{0.005}, T_2^{a**} > z_{0.0472/2}) \\
 &+ P(T_1 \leq z_{0.005}, T_1^a \leq z_{0.005}, T_2^{a*} > z_{0.0472/2}) \\
 &(\text{following similar logic in (1)}) = 0.005 + P(T_1^a \leq z_{0.005}, \sqrt{2/3}T_1^a + \sqrt{1/3}T > z_{0.0472/2}) \\
 &= 0.025
 \end{aligned}$$

- Under partitioned parameter spaces 7 or 8 (with j=1 or 2),

$$\begin{aligned}
 &P(\text{false rejection}) = P(\text{Reject } H_{0j}^{ORR} \text{ or } H_{01}^{PFS}) \\
 &= P(\text{Reject } H_{0j}^{ORR}) + P(\text{Reject } H_{01}^{PFS} \text{ but do not reject } H_{0j}^{ORR}) \\
 &\leq 0.0005 + P(T_1 > z_{0.005}, T_1^a > z_{0.005}, Z_1 > z_{0.015}) \\
 &+ P(T_1 > z_{0.005}, T_1^a \leq z_{0.005}, T_2^{a**} > z_{0.0462/2}, Z_2^{**} > z_{0.0323/2}) \\
 &+ P(T_1 \leq z_{0.005}, T_2^* > z_{0.0462/2}, T_2^{a*} > z_{0.0462/2}, Z_2^* > z_{0.0323/2}) \\
 &\leq 0.0005 + P(T_1 > z_{0.005}, T_1^a > z_{0.005}, Z_1 > z_{0.015}) \\
 &+ P(T_1 > z_{0.005}, T_1^a \leq z_{0.005}, T_2^{a**} > z_{0.0462/2}, Z_2^{**} > z_{0.0323/2}) \\
 &+ P(T_1 \leq z_{0.005}, T_2^{a*} > z_{0.0462/2}, Z_2^* > z_{0.0323/2}) \\
 &= 0.0005 + P(T_1 > z_{0.005}, T_1^a > z_{0.005}, Z_1 > z_{0.015}) \\
 &+ P(T_1 > z_{0.005}, T_1^a \leq z_{0.005}, T_2^{a**} > z_{0.0462/2}, Z_2^{**} > z_{0.0323/2}) \\
 &+ P(T_1 \leq z_{0.005}, T_1^a > z_{0.005}, T_2^{a*} > z_{0.0462/2}, Z_2^* > z_{0.0323/2}) \\
 &+ P(T_1 \leq z_{0.005}, T_1^a \leq z_{0.005}, T_2^{a*} > z_{0.0462/2}, Z_2^* > z_{0.0323/2}) \\
 &\leq 0.0005 + P(T_1 > z_{0.005}, T_1^a > z_{0.005}, Z_1 > z_{0.015}) \\
 &+ P(T_1 > z_{0.005}, T_1^a \leq z_{0.005}, Z_2^{**} > z_{0.0323/2}) \\
 &+ P(T_1 \leq z_{0.005}, T_1^a > z_{0.005}, Z_2^* > z_{0.0323/2}) \\
 &+ P(T_1 \leq z_{0.005}, T_1^a \leq z_{0.005}, Z_2^* > z_{0.0323/2}) \\
 &< 0.0005 + P(T_1 > z_{0.005}, T_1^a > z_{0.005}, (Z_1 > z_{0.015} \text{ or } Z_2^{**} > z_{0.0323/2})) \\
 &+ P(T_1 > z_{0.005}, T_1^a \leq z_{0.005}, (Z_1 > z_{0.015} \text{ or } Z_2^{**} > z_{0.0323/2})) \\
 &+ P(T_1 \leq z_{0.005}, T_1^a > z_{0.005}, (Z_1 > z_{0.015} \text{ or } Z_2^* > z_{0.0323/2})) \\
 &+ P(T_1 \leq z_{0.005}, T_1^a \leq z_{0.005}, (Z_1 > z_{0.015} \text{ or } Z_2^* > z_{0.0323/2})) \\
 &= 0.0005 + P(T_1 > z_{0.005}, (Z_1 > z_{0.015} \text{ or } Z_2^{**} > z_{0.0323/2})) \\
 &+ P(T_1 \leq z_{0.005}, (Z_1 > z_{0.015} \text{ or } Z_2^* > z_{0.0323/2}))
 \end{aligned}$$

$$\begin{aligned} & \text{(following similar logic in (1))} = 0.0005 + P(Z_1 > z_{0.015} \text{ or } \sqrt{2/3}Z_1 + \sqrt{1/3}T > z_{0.0323/2}) \\ & = 0.025 \end{aligned}$$

- Under partitioned parameter spaces 9, 10, 11, or 12 the false rejection rate is controlled by similar arguments as shown for partitioned parameter space 7 or 8.
- Under partitioned parameter spaces 13 or 14 (with $j=1$ or 2),
 $P(\text{False rejection}) = P(\text{Reject } H_{0j}^{ORR}) = 0.0005 < 0.025$

15.4 Time-to onset and time-to resolution definition and conventions for select adverse events, immune-mediated adverse events and other AEs of interest for NKTR-214

15.4.1 Time-to onset definition

Time-to onset of AE (any grade) for a specific category is defined as the time between the day of the first dose of study treatment and the onset date of the earliest AE (of any grade) in this category.

The time-to onset of AE (grade 3-5) for a specific category is defined similarly with an onset date corresponding to a grade 3-5 AE.

Time-to onset of drug-related AE (any grade or grade 3-5) for a specific category is defined similarly but restricted to drug-related AE.

Time-to onset for a specific subcategory is defined similarly but restricted to event of this subcategory.

15.4.2 Time-to resolution definition

In order to derive the time-to resolution, overlapping or contiguous AEs within a specific category or subcategory will be collapsed into what will be termed “clustered” AEs. For example, if a patient (without pre-treatment AE) experienced an AE from 1st to 5th January, another AE (with different PT but within same category) from 6th to 11th January and same AE from 10th to 12th January, these will be collapsed into one clustered AE from 1st to 12th January. [Table 8](#) is summarizing key derivation steps for each type of clustered AEs.

Time-to resolution of AE (any grade) for a specific category is defined as the longest time from onset to complete resolution or improvement to the grade at baseline among all clustered AEs experienced by the patient in this category per adverse event criteria category. Events which worsened into grade 5 events (death) or have a resolution date equal to the date of death are considered unresolved. If a clustered AE is considered as unresolved, the resolution date will be censored to the last known alive date. Improvement to the grade at baseline implies that all different events in the clustered adverse event should at least have improved to the corresponding

(i.e. with same preferred term) baseline grade. This measure is defined only for patients who experienced at least one AE in the specific category.

The time-to resolution of AE (grade 3-5) for a specific category is defined similarly with an onset date corresponding to a grade 3-5 AE.

Time-to resolution of drug-related AE (any grade or grade 3-5) for a specific category is defined similarly but restricted to drug-related AE.

The time-to resolution of AE (any grade or grade 3-5, drug-related or all) where immune modulating medication was initiated is defined similarly. For data presentation not restricted to IMAE, the additional condition that the patient started an immune modulating medication during the longest AE resolution period will be applied.

Time-to resolution for a specific subcategory is defined similarly but restricted to event of this subcategory.

Table 8: Derivation of Clustered AE

Type of clustered AE	Derivation
Any grade	Collapse any on-treatment AE from the same category
Drug-related of any grade	Collapse any on-treatment drug-related AE from the same category
Grade 3-5	Collapse any on-treatment AE from the same category. Resolution will be based on the onset date of the earliest grade 3-5 records (if no grade 3-5 record, clustered AE is excluded)
Drug-related of Grade 3-5	Collapse any on-treatment drug-related AE from the same category Resolution will be based on the onset date of the earliest grade 3-5 record (if no Grade 3-5 record, clustered AE is excluded)

The algorithm for collapsing adverse event records is using the following conventions:

For each patient and specified category, the corresponding adverse event records will be collapsed when:

- 1) Multiple adverse event records have the same onset date.
- 2) The onset date of an event record is either the same day or 1 day later than the resolution date of a preceding event record (contiguous events).
- 3) The onset date of an event record is after the onset date and prior to or on the resolution date of a preceding event record (overlapping events).

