EQ-5D-3L	X		X	X	X	Patients should complete the assessment at the start of the clinic visit, prior to dosing and scheduled activities.
FKSI-19	X		X	X	X	
PRO-CTCAE	X		X	X	X	Completed on Days 1 and 22 of every cycle through Cycle 4, and then on Day 1 of the following cycles. See Section 7.6 for further details.

Abbreviations used in this table appear on the final page of [Table 4](#).

Table 3: On-Treatment Schedule of Events for Arm B (Contd)

Procedure ^a	Arm B Cabozantinib 60 mg PO once daily (continuously) OR Sunitinib 50 mg PO once daily (4 weeks on treatment, followed by 2 weeks off treatment) Cycle = 6 Weeks					Notes
	Cycle 1			Cycle 2 and subsequent on-treatment visits		
	Day 1	Day 8 (-1 day)	Day 22 (± 3 days)	Day 1 (± 3 days)	Day 22 (± 3 days)	
Health Care Resource Utilization	X		X	X	X	Site staff will collect the health care resource utilization data at each visit using the CRF.

a. Assessments and visits that occur outside of protocol-specified windows (e.g., for holidays, travel issues, insurance issues) may be acceptable on a case-by-case basis after review by the Medical Monitor.

Abbreviations used in this table appear on the final page of [Table 4](#).

Table 4: Long-Term Follow-Up Schedule of Events

Procedure ^a	Safety Follow-Up Visit 1 ^b	Safety Follow-Up Visit 2 ^b	Survival Follow-Up ^c Every 12 Weeks (± 14 days)	Notes ^d
Safety Assessments				
Vital Signs	X	X		Blood pressure, heart rate, temperature Weight
AE and SAE Assessments	X	X	X	All AEs will be documented until 100 days after the last dose of all study drug(s). SAEs to be collected after the 100-day safety visit if the SAE is deemed to be related or residual toxicities are persisting. Patients will be followed for drug-related toxicities until these toxicities resolve, return to baseline, or are deemed irreversible.
Karnofsky Performance Status	X	X		See Appendix 2 .
Review of Subsequent Medications and Anticancer Therapy	X	X	X	In Survival Follow-up, subsequent anticancer treatment only. Additional subsequent anticancer therapy details such as regimen, setting of the regimen, line of therapy, start date and end date of each regimen, best response to the regimen, and date of progression to subsequent anticancer therapies will be collected.
Laboratory Tests				
Pregnancy Test (WOCBP only)	X	X		Patients (WOCBP) will continue to follow instructions for methods of contraception through 5 months post treatment completion.

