5.6.2 Survival Follow Up

- All patients will be contacted for survival every 12 weeks (\pm 14 days) following the Safety Follow-Up Visit 2 (or following last contact with the patient if Safety Follow-Up Visit 2 is missed).
- Survival visits may be conducted in person or by telephone.
- Information about subsequent anticancer therapy will also be collected during these contacts.
- The Sponsor may request that survival data be collected on all treated patients outside of the scheduled contacts. At the time of this request, each patient will be contacted to determine their survival status unless the patient has withdrawn consent for all contact or is lost to follow-up. Patients are not considered lost to follow up until after demonstration of due diligence with follow-up efforts. Alternative methods to determine survival status may be used (e.g., access to medical records and public record searches) as allowed by local regulations and/or guidelines.
- For patients who discontinue study treatment, radiographic tumor assessments will continue to be collected every 9 weeks (\pm 7 days) from randomization through (and inclusive of) Week 54 and then every 12 weeks (\pm 7 days) until both BICR and Investigator's assessments of tumor images have determined progression, patient withdraws consent, death, initiation of subsequent anticancer therapy, loss to follow up, or study termination by the Sponsor.
- Additional subsequent anticancer therapy details such as regimen, setting of the regimen, line of therapy, start date and end date of each regimen, best response to the regimen, and date of progression after next line of therapy will be collected.
- Survival follow up should continue until patient withdrawal of consent for survival follow up, death, loss to follow-up, or study termination by the Sponsor.

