8.5 AE Reporting and Follow-up

After initiation of study drug treatment, all AEs except for SAEs (Section 8.7 and 8.8) will be reported from the time of first study drug(s) administration until 100 days after the last dose of all study drug(s) (see Section 5.6).

All ongoing non-serious AEs will be followed until resolution, the patient is lost to follow-up, patient death, or until the last Safety Follow-Up Visit. If the AE has not completely resolved by the last Safety Follow-Up Visit, the final outcome of these ongoing AEs will be captured as "Not Recovered/Not Resolved" or "Recovering/Resolving", whichever is applicable.

For specific instructions on identifying and reporting SAEs, see Sections 8.6 and 8.7.

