8.8 Serious AE Follow-up

All study treatment-related SAEs that have not resolved by the last Safety Follow-Up visit (Section 5.6) will be followed until any of the following occur (whichever comes first):

- The event resolves.
- The event has stabilized.
- The event returns to baseline, if a baseline value is available.
- It is unlikely that any additional information can be obtained (e.g., patient or health care practitioner refuses to provide additional information; lost to follow-up after demonstration of due diligence with follow-up efforts).
- The patient dies or is lost to follow-up.

All ongoing SAEs assessed as unrelated to study drug(s) will be followed until resolution or until the last Safety Follow-Up Visit (Section 5.6.1), whichever is earlier. In the case where an unrelated SAE has not completely resolved by the last Safety Follow-Up Visit, the final outcome of these ongoing unrelated SAEs will be captured as “Not Recovered/Not Resolved” or “Recovering/Resolving”, whichever is applicable.

8.9 Disease Progression and Death Due to Disease Progression – Not Reportable as an AE/SAE

It is anticipated that during this study a proportion of patients will experience disease progression prior to study discontinuation. Disease progression should not be reported as an AE or SAE. In some patients, disease progression may result in clinical manifestations (e.g., pleural effusion) that meet “seriousness” criteria (e.g., hospitalization). These manifestations may be reported as non-fatal SAEs.

For all SAEs assessed as clinical manifestations associated with fatal disease progression, the following criteria will apply:

- Seriousness Criteria cannot equal Death
- Severity cannot equal Grade 5
- Outcome = Ongoing at time of Death

Deaths that are attributed solely to disease progression by the Investigator should not be reported as SAEs.

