For patients off treatment, the treatment-emergent period is defined as the period of time on or after the day (and time, if collected and not missing) of the first dose of study treatment, until: the date of (initiation of new anticancer therapy – 1 day) or (30 days after the date of the last dose of any study treatment), whichever is earlier.

The extended treatment-emergent period will be defined as the period of time on or after the day (and time, if collected and not missing) of the first dose of study treatment until earlier date of (initiation of new anticancer therapy – 1 day) and (100 days after the date of the last dose of any study treatment).

- **Treatment-Emergent Adverse Event (TEAE):**

TEAEs are AEs with an onset date (and time, if collected and not missing) within the treatment-emergent period, or extended treatment-emergent period depending on the analysis

Incomplete start and end dates for TEAEs will be imputed. Any AE will be considered as a TEAE if its status cannot be fully determined because of incomplete data.

- **Last Known Alive Date:** Last known alive date will be defined as the latest alive date on or before data cutoff date, captured from multiple sources. Note that if there is an event date (either an assessment or death) beyond the data cutoff date, the last known alive date will be the data cutoff date. If a patient died before or on the data cutoff date, the last known alive date will be set as the death date. The last known alive date will not be imputed, except in the case that the death date is partially missing (see details in Section 6.4)

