8.2.1.3 Time-to Resolution of Drug-Related Select AE

Time-to resolution of the following specific events will be summarized separately for each category/subcategory by treatment arm.

- Time-to resolution of drug-related select AE (any grade, grade 3-5)
- Time-to resolution of drug-related select AE (any grade, grade 3-5) where immune modulating medication was initiated

Time-to resolution analyses are restricted to treated patients who experienced the specific events. Time-to resolution where immune-modulating medication was initiated analyses are restricted to treated patients who experienced the specific events and who received immune-modulating medication during the longest select AE.

The following summary statistics will be reported: percentage of patients with resolution of the longest select AE, median time-to resolution along with 95% CI (derived from Kaplan-Meier estimation) and ranges.

Additional details regarding the time-to resolution definition are described in Appendix Section [15.4.2](#).

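### Unresolved select and immune-mediated AEs are censored at the last known alive date, although follow-up of some of them closes at the 100-day safety visit, so time to resolution can be overstated

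*SAP*

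**What the plan says.** **Analysis.** SAP 15.4.2 defines time to resolution as the longest clustered event in a category and adds: "If a clustered AE is considered as unresolved, the resolution date will be censored to the last known alive date". SAP 6.6 defines that date broadly: "Last known alive date will be defined as the latest alive date on or before data cutoff date, captured from multiple sources". SAP 8.2.1.3 reports the percentage of patients whose longest event resolved and the "median time-to resolution along with 95% CI (derived from Kaplan-Meier estimation) and ranges". That section is restricted to drug-related select AEs. SAP 8.2.2 plans time to resolution for IMAEs in Arm A, and there causality is not a criterion.

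**Follow-up.** Protocol 8.5 makes no distinction by causality: "All ongoing non-serious AEs will be followed until resolution, the patient is lost to follow-up, patient death, or until the last Safety Follow-Up Visit". It then closes the record: "If the AE has not completely resolved by the last Safety Follow-Up Visit, the final outcome of these ongoing AEs will be captured as" not recovered or recovering. Protocol 8.8 treats unrelated serious events alike: "All ongoing SAEs assessed as unrelated to study drug(s) will be followed until resolution or until the last Safety Follow-Up Visit". Treatment-related SAEs stay open under 8.8 beyond that visit. In Protocol 1.2, Table 4 marks AE and SAE assessment in the survival follow-up column and states: "Patients will be followed for drug-related toxicities until these toxicities resolve, return to baseline, or are deemed irreversible". Section 5.6.1 has a similar sentence but refers to 8.5 and 8.8 for how this is done. Vital status continues separately under 5.6.2: "All patients will be contacted for survival every 12 weeks", in person or by telephone.

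**The concern.** A patient should leave the risk set when the event can no longer be seen to happen. Once an AE record is closed with a final outcome, a later resolution is not captured, yet under 15.4.2 the patient stays at risk of resolution for as long as survival contacts show the patient alive. Kaplan-Meier reads that time as time observed without resolution.

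The SAP follows the usual principle elsewhere. PFS and duration of response are censored at the last evaluable tumor assessment, and ADA duration at the last ADA-evaluable assessment. Only AE resolution takes a vital-status date for a state that may no longer be assessed.

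At stake are the medians, curves and ranges describing how long immune-type toxicity lasts. SAP 8.2.1 and 8.2.2 label these tables as support for the EU and US marketing applications. Slow-resolving categories are the most exposed.

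**Working it through.** The documents give no time-to-resolution figure to reproduce. The check has three parts: which events are affected, in which direction, and by how much.

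**1. Which events are affected**

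| Event | Enters | Protocol ends follow-up at | Unobserved time counted? |
|---|---|---|---|
| Treatment-related SAE | select AE, IMAE | 8.8: beyond the last safety visit, until resolved, stabilized, back to baseline, no more information, death or loss | Little |
| Non-serious, drug-related | select AE, IMAE | 8.5: last safety visit; Table 4 and 5.6.1: later | Yes if 8.5 governs |
| Non-serious, unrelated | IMAE only | 8.5: last safety visit | Yes |
| Unrelated SAE | IMAE only | 8.8: last safety visit | Yes |

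The two dates nearly coincide for patients still on treatment or within 100 days of last dose at cutoff, and for those who die in that window.

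**2. Direction (ten invented patients)**

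Six events resolve on days 10, 20, 30, 60, 150 and 200. Four are unresolved when AE follow-up closes on day 100. Those four patients are last known alive on days 400, 450, 500 and 600. After day 60 the share unresolved is 6/10 = 0.60 under both rules.

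- Censored on day 100: two are at risk on day 150, so 0.60 × 1/2 = 0.30; on day 200, 0.30 × 0/1 = 0.
- Censored at last known alive: six are at risk on day 150, so 0.60 × 5/6 = 0.50; on day 200, 0.50 × 4/5 = 0.40.

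The curve is higher and the longest censored time goes from 100 to 600 days. The median, taken as the first time the curve is at or below 0.50, is day 150 either way. Moving a censoring time later can only enlarge later risk sets, so the curve rises or stays where it is.

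**3. Size (simulation; every input is an assumption except the 100 days and the 104-week cap on treatment)**

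Inputs: median treatment 30 weeks, capped at 104; onset uniform over treatment; exponential resolution; median survival 41 months; data cut 24 to 45 months after start; AE follow-up to last dose + 100 days, except for a share followed to the last known alive date. Censoring at the true end of observation returns 12, 26 and 40 weeks. The SAP rule returns these medians, in weeks:

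| True median | 0% followed on | 50% | 75% | 90% |
|---|---|---|---|---|
| 12 | 12 | 12 | 12 | 12 |
| 26 | 39.5 | 29 | 27 | 26 |
| 40 | not reached | 54 | 45 | 42 |

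With 0% followed on, the share unresolved at 52 weeks is 23% instead of 5%, 48% instead of 25%, and 61% instead of 41% for the three true medians.

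The 12-week median stays put because an event starting on treatment is observed for at least 100/7 = 14.3 weeks, short of death or cutoff. The onset assumption matters: allowing onset up to 30 days after last dose raises the worst-case 26-week result to about 61 weeks.

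A second simulation used other assumptions: 30% stop drug at onset, the rest continue for a mean of 180 days, then 100 days of AE follow-up and 0 to 600 days of survival follow-up. Medians with censoring at end of AE follow-up versus last known alive were 30 vs 30, 90 vs 90, 182 vs 317, and 368 days vs not reached. If every patient stops at onset, all are observed for the same 100 days and the two rules give the same median and the same day-180 estimate.

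**The case against.** The best defense is that the protocol does plan to follow drug-related toxicity past Day 100. Table 4 and 5.6.1 say so, 8.8 keeps treatment-related SAEs open, and select-AE time to resolution contains only drug-related events. Where that follow-up happens, the last known alive date is a defensible censoring date. This stands for treatment-related SAEs. For non-serious drug-related events it is unsettled, because 5.6.1 refers back to 8.5, and 8.5 closes them.

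A reader might infer that no resolution after Day 100 can ever be recorded, or that many IMAEs lack extended follow-up. Neither is supported. The first is untrue for treatment-related SAEs. On the second, an IMAE must also have no clear alternate etiology or have an immune-mediated component, and non-endocrine IMAEs must have been treated with immune-modulating medication. SAP 8.1 counts a missing relationship as related. IMAEs judged unrelated may be few; the documents give no number.

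It is also fair that the percentage resolved does not change when a patient has one cluster in the category. With several clusters it can fall, because 15.4.2 selects the longest and a stretched unresolved cluster can displace a resolved one.

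Finally, censoring at the last recorded status has its own risk. Follow-up may stop because an event is judged irreversible (Table 4) or stabilized (8.8). Removing those patients would be informative and could shorten the estimate. The fix has to allow for this.

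**Conclusion.** The mismatch is real but limited. It is clear for IMAEs judged unrelated. It extends to non-serious drug-related select AEs and IMAEs only if Protocol 8.5 governs over Table 4 and 5.6.1. In those groups the Kaplan-Meier curve and the upper range can be overstated, and cannot be understated relative to censoring at the end of observation.

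A reader might go further and conclude that all the planned medians are biased upward. The documents do not support that: the effect depends on the share of events followed past Day 100, which they do not give, and fast-resolving categories may show no change in the median. The 39.5-week result for a true 26 weeks, and the result of not reached for a true 40, are worst cases within the stated onset assumption, since they require that no event is followed past Day 100.

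These are descriptive safety tables. No primary or key secondary test, and no alpha, depends on them. The rule should be corrected because the remedy is small and the tables are meant for submission.

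**What to change.** **SAP 15.4.2.** Censor an unresolved clustered AE at the earlier of the last known alive date and the end of AE follow-up for that event: Safety Follow-Up Visit 2, or last dose + 100 days if that visit is missed. Where the site followed a drug-related event longer, use the last date its status was recorded, if collected. The AE items listed in Protocol 8.2 do not name such a date, so check the case report form first. Events whose follow-up ended because they were deemed irreversible or permanent should remain unresolved to the last known alive date. State explicitly how a treatment-related SAE closed as stabilized under 8.8 is handled. Apply the same rule to select AEs and IMAEs. Data cutoff need not be listed, because SAP 6.6 already caps the last known alive date there. The current rule can be kept as a sensitivity analysis.

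**Protocol.** Reconcile 8.5 with 5.6.1 and Table 4 on how long non-serious drug-related events are followed.

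**Cost.** A short SAP text change and a small programming change; some patients will be censored earlier.
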